1. MTX
2. Upadacitinib 15 mg QD
3. Upadacitinib 30 mg QD
4. Upadacitinib 15 mg QD + MTX
5. Upadacitinib 30 mg QD + MTX

For Japan sub-study, there are two additional treatment regimens:

6. Upadacitinib 7.5 mg QD
7. Upadacitinib 7.5 mg QD + MTX

Among the subjects who entered Period 2 participation (regardless of whether subject prematurely discontinued study drug in Period 1), the number and percentage of subjects who completed, and who prematurely discontinued study participation in Period 2 will be summarized. Among the subjects who entered Period 2 upon completion of study drug in Period 1, the number and percentage of subjects completed, and who prematurely discontinued study drug in Period 2 will be summarized.

For subjects who prematurely discontinued study drug or study participation, the primary reasons as well as all reasons for discontinuation will be summarized by the following categories (as collected in CRF):

- Adverse event (AE)
- Withdrew consent
- Lost to follow-up
- Lack of efficacy
- Other

Summary of Dose Switch from Upadacitinib 30 mg QD to 15 mg QD

Starting with Amendment 5.01.01 (for Japan) and Amendment 6 (for global), subjects receiving upadacitinib 30 mg QD will be switched to upadacitinib 15 mg QD. The visit at which dose switch occurs could be different for each subject. For subjects on upadacitinib 30 mg QD in Period 2, the number and percentage of subjects switching to upadacitinib 15 mg QD at each visit will be summarized.

8.0 Study Drug Exposure and Compliance

8.1 Study Drug Exposure

The duration of exposure to study drug will be summarized for the safety analysis set by the following groups.

1. MTX monotherapy

This includes MTX exposure as monotherapy from subjects starting on MTX monotherapy censored at time of rescue to upadacitinib + MTX.

2. Any Upadacitinib 15 mg QD

This includes Upadacitinib 15 mg QD exposure from subjects starting on Upadacitinib 15 mg QD and subjects rescued from MTX to Upadacitinib 15 mg QD + MTX.

3. Upadacitinib 15 mg QD mono

This includes Upadacitinib 15 mg QD monotherapy exposure from subjects starting on Upadacitinib 15 mg QD monotherapy and censored at time of rescue to upadacitinib 15 mg QD + MTX or with addition of background csDMARD.

4. Any Upadacitinib 30 mg QD

This includes Upadacitinib 30 mg QD exposure from subjects starting on Upadacitinib 30 mg QD and subjects rescued from MTX to Upadacitinib 30 mg QD + MTX. Exposure is censored at time of dose switch from Upadacitinib 30 mg QD to Upadacitinib 15 mg QD.

5. Upadacitinib 30 mg QD mono

This includes Upadacitinib 30 mg QD monotherapy exposure from subjects starting on Upadacitinib 30 mg QD monotherapy and censored at time of rescue to upadacitinib 30 mg QD + MTX or with addition of background csDMARD. In addition, exposure is censored at time of dose switch from Upadacitinib 30 mg QD to Upadacitinib 15 mg QD.

6. Any Upadacitinib 15 mg QD switched from any Upadacitinib 30mg QD

This includes Upadacitinib 15 mg QD exposure from subjects who switched dose from Upadacitinib 30 mg QD to Upadacitinib 15 mg QD.

7. Upadacitinib 15 mg QD mono switched from Upadacitinib 30mg QD mono

This includes Upadacitinib 15 mg QD monotherapy exposure from subjects who started and remained on Upadacitinib 30 mg QD monotherapy (without rescue or addition of background csDMARD) and switched dose from Upadacitinib 30 mg QD to Upadacitinib 15 mg QD. Exposure is censored at time of addition of background csDMARD.

In addition to the groups above, the Japan sub-study has the additional groups of Any Upadacitinib 7.5 mg QD and Upadacitinib 7.5 mg QD monotherapy.

Subjects could be blindly switched from Upadacitinib monotherapy to the combination of upadacitinib + MTX at Week 26, or could have background csDMARD added/initiated after Week 26, depending upon the CDAI response and joint counts. For subjects rescued with blinded study drug MTX at Week 26, the exposure under upadacitinib monotherapy is censored prior to the day when blinded study drug MTX is initiated. For subjects not rescued with blinded study drug MTX at Week 26 but added/initiated csDMARD as a background therapy, the exposure under the monotherapy of upadacitinib is censored prior to the day when the first dose of csDMARD is initiated.

Starting with Amendment 5.01.01 (for Japan) and Amendment 6 (for global), subjects receiving upadacitinib 30 mg QD will be switched to receiving upadacitinib 15 mg QD. Exposure to upadacitinib 30 mg QD (Groups 4 and 5) will be censored prior to the day subject received the first dose of upadacitinib 15 mg QD, and subsequent exposure to upadacitinib 15 mg QD will be summarized under separate groups (Groups 6 and 7).

The duration of exposure to study drug will be summarized for each group as specified above, with the number of subjects, mean, standard deviation, median, minimum and maximum values. In addition, the number and percentage of subjects exposed to study drug will be summarized for the following cumulative duration intervals.

- ≥ 2 weeks
- ≥ 1 month
- ≥ 3 months
- ≥ 6 months
- ≥ 9 months
- ≥ 12 months
- ≥ 18 months
- ≥ 2 years
- ≥ 2.5 years
- ≥ 3 years
- ≥ 4 years

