 - but achieve $\geq 20\%$ improvement in both TJC and SJC compared with baseline will continue on blinded MTX and the Investigator should optimize (initiate or increase) background RA medications: NSAIDs, corticosteroids (oral ≤ 10 mg/day prednisone equivalent and up to 2 local injections), low-potency analgesics and csDMARDs (only 1 of the following: sulfasalazine, hydroxychloroquine or chloroquine) throughout the remainder of Period 1 and until the study is unblinded.
 - and do not achieve $\geq 20\%$ improvement in both TJC and SJC compared with baseline will be re-randomized in a 1:1 ratio to receive blinded upadacitinib 15 mg QD or upadacitinib 30 mg QD (for subjects in Japan: randomize 1:1:1 to receive upadacitinib 7.5 mg QD, 15 mg QD, or 30 mg QD) while continuing MTX treatment in a blinded manner and will remain on upadacitinib plus MTX throughout the remainder of Period 1 and until the study is unblinded.
 - Those who achieve Clinical Remission (CR) by clinical disease activity index (CDAI) (CDAI ≤ 2.8) at Week 26 will continue blinded treatment with MTX throughout the remainder of Period 1 and until the study is unblinded (the study is unblinded when all subjects have completed Period 1).
2. Subjects who were originally randomized to Upadacitinib:
 - Those who do not achieve CR by CDAI:

- but achieve $\geq 20\%$ improvement in both TJC and SJC compared with baseline will continue on blinded upadacitinib and the Investigator should optimize (initiate or increase) background RA medications: NSAIDs, corticosteroids (oral ≤ 10 mg/day prednisone equivalent and up to 2 local injections), low potency analgesics and csDMARDs (only 1 of the following: sulfasalazine, hydroxychloroquine or chloroquine) throughout the remainder of Period 1 and until the study is unblinded.
- and do not achieve $\geq 20\%$ improvement in both TJC and SJC compared with baseline will add MTX 10 mg/week (7.5 mg for China and Japan) to upadacitinib in a blinded manner and will remain on upadacitinib plus MTX 10 mg/week (7.5 mg for China and Japan) throughout the remainder of Period 1 and until the study is unblinded.
- Those who achieve Clinical Remission (CR) by CDAI ($CDAI \leq 2.8$) at Week 26 will continue blinded treatment with upadacitinib throughout the remainder of Period 1 and until the study is unblinded (the study is unblinded when all subjects have completed Period 1).

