10.1.2 Long Term Safety Analysis

Long-term safety analyses include reporting of AE rate adjusted by cumulative exposure, mean change from baseline in laboratory parameters and vital sign variables, and frequency of potentially clinically significant laboratory and vital signs values. The

treatment-emergent adverse event (TEAE) rate per 100 patient-years of exposure will be presented by actual treatment received (i.e., exposed to) at the time of AE (as described in Section 10.2.2), where treatment exposure groups are described in Section 8.1. Listing of subjects with TEAEs by SOC and PT will be provided. Frequency tables and listings of subjects meeting criteria for potentially clinically significant vital sign values and for potentially clinically significant laboratory values will be provided by actual treatment received at the time of event. Mean changes from baseline in all continuous laboratory parameters and vital signs variables at each visit will be summarized by "as treated" exposure sequences defined as follows:

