1. MTX
2. Upadacitinib 15 mg QD
3. Upadacitinib 30 mg QD
4. MTX → Upadacitinib 15 mg QD + MTX
5. MTX → Upadacitinib 30 mg QD + MTX
6. Upadacitinib 15 mg QD → Upadacitinib 15 mg QD + MTX/csDMARD
7. Upadacitinib 30 mg QD → Upadacitinib 30 mg QD + MTX/csDMARD

For Japan sub-study, there are three additional exposure sequences:

8. Upadacitinib 7.5 mg QD
9. MTX → Upadacitinib 7.5 mg QD + MTX
10. Upadacitinib 7.5 mg QD → Upadacitinib 7.5 mg QD + MTX/csDMARD

Starting with Amendment 5.01.01 (for Japan) and Amendment 6 (for global), subjects receiving upadacitinib 30 mg QD will be switched to upadacitinib 15 mg QD. For these subjects, adverse events and exposure to upadacitinib 30 mg QD will be censored at the time of dose switch; subsequent adverse events and exposure starting the day of first dose

of upadacitinib 15 mg QD will be summarized under separate groups, as described in Section 8.1. Assessment of potentially clinically significant laboratory and vital sign values will be based on the same treatment exposure groups as for adverse events, as described above. For summary of mean change from baseline in laboratory values and vital signs, exposure sequences 3, 5 and 7 (i.e., subjects who switched from upadacitinib 30 mg QD to 15 mg QD) will be censored at the time of dose switch. Mean change from baseline for laboratory values and vital signs collected after dose switch will be summarized separately by visits post switch.

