10.2.2.1 Overview of Adverse Events Rates per 100 Patient-Years of Study Drug Exposure

An overview of AEs per 100 patient-years of study exposure will be presented by treatment group and overall for the following AE categories.

- All TEAEs
- Treatment-emergent serious adverse events (SAEs)
- Treatment-emergent severe adverse events
- TEAEs reasonably possibly related to study drug
- TEAEs of special interest
- TEAEs leading to discontinuation of study drug
- TEAE leading to death

For this calculation, one year will be considered to be 365.25 days. For each treatment group, the numerator of the overall rate will be the total number of TEAEs reported for the event; that is, a subject can contribute more than one event to the numerator. For each treatment group, the denominator of the rates will be the total number of days exposed to study drug summed across all treated subjects divided by 365.25. The TEAE rate per 100 patient-years of exposure will be calculated as $(\text{[numerator/denominator]}) * 100$. The number of TEAEs reported (numerator), the total number of years of study drug exposure (denominator), and the TEAE rate per 100 patient-years will be presented for each treatment group and overall.

In the AE overview summary, any event with an unknown severity will be considered as severe and any AE with an unknown relationship will be considered as having "reasonable possibility" of being related to study drug. Additional TEAEs may be

considered for tabulation/summary based on recommendations from Clinical and Safety as deemed appropriate.

For TEAEs of special interest, the point estimate and 95% CI (using normal approximation) will be provided for the treatment difference in the TEAE rate per 100 patient years between each Upadacitinib dose group and the MTX group.

As a sensitivity analysis, the AE overview summary per 100 patient-years of study exposure will be repeated by exposure groups. In this summary, all AEs with an onset date after the first dose of study drug will be included, regardless of whether the AE occurred more than 30 days after the last dose of study drug. This sensitivity analysis will only be performed in final CSR.

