11.0 Summary of Changes

11.1 Summary of Changes between the Previous Version and the Current Version

The primary efficacy analysis and Period 1 reporting have been completed under the SAP version 2.0. The current SAP update applies only to future reporting of long term analysis.

1. Updated throughout the SAP to align with Protocol Amendment 6, including handling of dose switch from upadacitinib 30 mg QD to 15 mg QD (hereafter referred to as "dose switch").
2. Updated Section 7.0 to clarify analysis details and incorporate additional summary of dose switch.
3. Updated Section 8.0 study drug exposure groups to accommodate dose switch.
4. Updated Section 9.1 to clarify the definition of treatment group sequences.
5. Updated Sections 9.1 and Section 9.4 to incorporate handling of dose switch for long-term efficacy analysis.
6. Updated Section 9.1.1 to describe the missing data handling approach for the additional sensitivity analysis using longitudinal models for long-term efficacy.
7. Updated Section 9.4 to incorporate the additional sensitivity analysis for long-term efficacy.
8. Added language to clarify analysis details in Sections 10.2.1.1, Section 10.2.2.1, Section 10.2.2.3.
9. Updated Sections 10.2.1.6 and Section 10.4.1 to align with the latest upadacitinib AESI definitions in PSSAP V4.0.
10. Updated Section 10.1.2, Section 10.2.2, Section 10.2.2.1, Section 10.3.3.1, Section 10.3.3.2, Section 10.3.3.3 and Section 10.4.3 to incorporate handling of dose switch for long-term safety analysis.

11. Updated Section 10.1.2, Section 10.3.3.1 and Section 10.4.3 to clarify the use of exposure sequences.
12. Added Appendix B to describe analysis accounting for impact of COVID-19 pandemic.

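### SAP 8.1 censors upadacitinib monotherapy, but not MTX monotherapy, when a background csDMARD is added, so long-term comparisons of the two monotherapy groups use unmatched follow-up

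*SAP*

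**What the plan says.** SAP 8.1 defines the exposure groups used for long-term safety. Group 1, MTX monotherapy: "This includes MTX exposure as monotherapy from subjects starting on MTX monotherapy censored at time of rescue to upadacitinib + MTX". Group 3, upadacitinib 15 mg monotherapy, has two censoring events; it is "censored at time of rescue to upadacitinib 15 mg QD + MTX or with addition of background csDMARD". Group 5 (30 mg monotherapy) has the same two events plus the dose switch. Group 7 (monotherapy after the switch from 30 to 15 mg) is also censored at csDMARD addition. The explanatory text after the list repeats the csDMARD rule for one drug only: "the exposure under the monotherapy of upadacitinib is censored prior to the day when the first dose of csDMARD is initiated".

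MTX subjects can reach that state. At Week 26, those not in CDAI remission who have at least 20% joint-count improvement "will continue on blinded MTX and the Investigator should optimize (initiate or increase) background RA medications", and the list of medications includes one of sulfasalazine, hydroxychloroquine or chloroquine (SAP 4.2). Weeks 36 to 40 bring a similar option in all arms. From Week 48, csDMARD addition is open in all arms (Protocol 5.1 and 5.2.3.1).

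Under SAP 10.1.2 the long-term TEAE "rate per 100 patient-years of exposure will be presented by actual treatment received (i.e., exposed to) at the time of AE", using the 8.1 groups. For events of special interest, SAP 10.2.2.1 adds a point estimate and 95% CI for the "treatment difference in the TEAE rate per 100 patient years between each Upadacitinib dose group and the MTX group". SAP 10.3.3.2, 10.3.3.3 and 10.4.3 use the same groups for potentially clinically significant laboratory values, liver elevations and vital signs.

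**The concern.** Two groups both labelled monotherapy are built by different rules. Once a csDMARD is added, an upadacitinib subject leaves the monotherapy group and an MTX subject stays in it. Subjects who add one are selected: at Week 26 they are not in CDAI remission, and at Weeks 36 to 40 they have failed the joint-count criterion at two consecutive visits. If their later event rate differs from that of subjects who stay on a single drug, the MTX rate moves and the upadacitinib monotherapy rate does not.

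At stake is how the monotherapy columns of the long-term safety tables are read against each other, over follow-up of up to 260 weeks. That reporting can still be changed. SAP 11.1 says of version 3.0: "The current SAP update applies only to future reporting of long term analysis".

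**Working it through.** **1. The rules side by side (SAP 8.1).**

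| Group | Censored at rescue with added study drug | Censored at csDMARD addition |
|---|---|---|
| 1. MTX monotherapy | yes | not stated |
| 3. Upadacitinib 15 mg mono | yes | yes |
| 5. Upadacitinib 30 mg mono | yes | yes |
| 7. 15 mg mono after 30 mg mono | rescued subjects not included | yes |
| 2, 4. Any Upadacitinib | no | no |

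Groups 4 and 5 are also censored at the 30 to 15 mg dose switch. There is no MTX plus csDMARD group. The exposure sequences in SAP 10.1.2 follow the same pattern: "Upadacitinib 15 mg QD → Upadacitinib 15 mg QD + MTX/csDMARD" has no MTX counterpart. Those sequences serve only mean-change summaries of laboratory values and vital signs.

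**2. Which pairings are affected.** Mono versus group 1 is unmatched: csDMARD time is dropped on one side and kept on the other. 'Any Upadacitinib' versus group 1 keeps csDMARD time on both sides. If group 1 were instead read as excluding csDMARD time, the mono pairing would match and the 'Any' pairing would not. One MTX group therefore cannot match both kinds of upadacitinib group.

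**3. Illustration of size.** The plan gives no figure to reproduce. Let f be the share of group 1 person-time after csDMARD addition, and r the event rate in that time relative to MTX alone. Neither is in the documents, so both are assumptions.

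Reported MTX rate ÷ rate on MTX alone = (1 − f) + f·r = 1 + f(r − 1).

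| f | r = 0.8 | r = 1.0 | r = 1.2 | r = 1.5 |
|---|---|---|---|---|
| 10% | 0.98 | 1.00 | 1.02 | 1.05 |
| 20% | 0.96 | 1.00 | 1.04 | 1.10 |
| 30% | 0.94 | 1.00 | 1.06 | 1.15 |
| 40% | 0.92 | 1.00 | 1.08 | 1.20 |

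Suppose the true rates on upadacitinib alone and MTX alone are equal. The reported upadacitinib-mono to MTX rate ratio is then the reciprocal of the table entry:

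- f = 20%, r = 1.5: 1/1.10 = 0.909.
- f = 40%, r = 1.5: 1/1.20 = 0.833.
- f = 20%, r = 0.8: 1/0.96 = 1.042.
- r = 1: 1, so no bias.

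At an assumed 3.0 events per 100 patient-years on MTX alone, f = 40% and r = 1.5 give 3.0 × 1.20 = 3.60, a spurious difference of −0.60. With f = 40% and r = 0.8, 3.0 × 0.92 = 2.76, a spurious difference of +0.24.

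**4. Can the documents narrow f?** No. csDMARDs may be added from Week 26 to Week 260, (260 − 26)/260 = 90% of the treatment period, but that is permission and not use. The planned Week 24 remission rates do not help either: they use DAS28 and not CDAI, they leave in subjects rescued to upadacitinib + MTX (who are censored from group 1), and an instruction to optimize can be met with NSAIDs, steroids or analgesics alone.

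**The case against.** **The word monotherapy already excludes csDMARD time.** This is a fair reading of the label. But the same sentence names its one censoring event, while groups 3, 5 and 7 each carry an explicit csDMARD clause and the explanatory paragraph covers upadacitinib only. Two programmers could produce different denominators. If exclusion is intended, one clause settles it.

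**There may be a reason for the difference.** MTX is itself a csDMARD, so adding sulfasalazine does not bring a new drug class into that arm. Period 2 options also differ: after unblinding, a subject not on MTX may add up to two csDMARDs, including MTX or leflunomide, whereas MTX and leflunomide may not be combined (Protocol 5.2.3.1). Without csDMARD censoring, upadacitinib mono could contain upadacitinib plus open-label MTX. This justifies censoring upadacitinib. It does not justify calling MTX plus a second csDMARD monotherapy.

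**A matched comparison already exists.** This stands for the csDMARD mismatch. A reader might infer that the whole long-term safety comparison is not like for like, and the SAP does not support that: 'Any Upadacitinib' versus MTX keeps csDMARD time on both sides, and 10.2.2.1 does not say which pairing carries the interval. But 'Any Upadacitinib' also includes upadacitinib + MTX time, so it does not replace a monotherapy comparison.

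**Matched censoring is not unbiased.** This also stands. Subjects who add a csDMARD are selected for insufficient response, so censoring them is informative in both arms.

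**Conclusion.** The point holds for the monotherapy pairing. As SAP 8.1 is written, MTX plus csDMARD person-time and events are reported as MTX monotherapy, while the corresponding upadacitinib time is removed. Long-term AE rates, potentially clinically significant laboratory values and vital signs, and liver elevations are all affected when upadacitinib mono is set against MTX monotherapy.

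A reader might infer that the mismatch makes upadacitinib look safer. The documents do not show that. It would do so if r exceeds 1, do nothing if r equals 1, and do the opposite if r is below 1. Under the assumed f of 10% to 40% and r of 0.8 to 1.5, the reported MTX rate is 0.92 to 1.20 times the rate on MTX alone.

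Nor is this a clear breach of the rule to report by actual treatment received. SAP 10.1.2 ties that rule to the 8.1 groups, and 'Any Upadacitinib' itself keeps csDMARD time. The problem is that adjacent columns use the word monotherapy in different senses.

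Safety analyses up to Week 26 and the randomized-group efficacy analyses do not use these groups. Completed Period 1 reporting is not reopened. The affected comparisons are descriptive, with no hypothesis test planned. It should be fixed before the long-term tables are produced.

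**What to change.** 1. In SAP 8.1 group 1, add csDMARD addition as a second censoring event, in the same terms as groups 3 and 5, and extend the explanatory csDMARD sentence to MTX.
2. Keep the present definition as a second group, labelled *MTX with or without background csDMARD*.
3. In SAP 10.2.2.1, state the pairings: upadacitinib monotherapy against the censored MTX group, and 'Any Upadacitinib' against the uncensored one.
4. Report the person-years censored for csDMARD addition in each arm, so that readers can judge how much follow-up the rule removes.

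An MTX to MTX + csDMARD sequence in SAP 10.1.2 is optional, since those sequences serve only mean-change summaries.

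The cost is one extra column and some re-programming. Start dates of concomitant medications are already collected (Protocol 5.2.3), and csDMARD start must already be derived for groups 3, 5 and 7. Keeping the present definition preserves continuity with earlier reports. The limitation is that matched censoring remains informative in both arms, so the monotherapy comparison should still be presented as descriptive.

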8.2 Compliance

Study drug compliance for Upadacitinib/PBO and for MTX/PBO will be summarized separately for each treatment group up to Week 24. Upadacitinib/PBO compliance is defined as the number of Upadacitinib/PBO tablets taken (i.e., the difference between the number of tablets dispensed and the number of tablets returned) during the subject's participation up to Week 24 divided by the number of days that the subject was in the Treatment Phase up to Week 24. MTX/PBO compliance is defined as the number of MTX doses taken during the subject's participation up to Week 24 divided by the number of weeks that the subject was in the Treatment Phase up to Week 24.

